The study subjects will engage in an A (upper extremities FES assisted ergometry)-B (upper extremities non-FES assisted exercises) type protocol intervention in which they undergo either 4 months of FES assisted upper extremity ergometry followed by 1 month wash out period, then by 4 months of a specific, individualized, non-FES assisted exercise regimen (strengthening, stretching, splinting) or 4 months of an upper extremities non-FES assisted exercise protocol followed by 1 month wash out period, then by 4 months of FES assisted upper extremity ergometry. 12 subjects randomly selected will start with the FES assisted intervention and the other 12 subjects will start with the non FES assisted regimen. FES will be delivered using the RT300-SLSA Cycle Ergometer, Restorative Therapies, Inc. The subjects will be assessed using a battery of physical and neurological indicators before starting the intervention (time 0), after completing first 4 months of intervention (4 months), after the 1 month wash out (5 months), after completing the second 4 month of intervention (9 months) and 3 months after completing the last intervention (12 months). The evaluator will be blinded to group assignment, but we cannot use true blinding due to the intervention's sensory component. The Study Time Line is found in Figure 1.

[figure not shown]

Figure 1: Study Time Line

(1) Assessment:

The tests listed below will be performed for all subjects. The data collection schedule in Table 1.

a) Neurological Exam: This is a routine exam performed to rule out any associated lower motor neuron/peripheral nerve injury in the C1-C6 levels. Subjects will undergo testing of the deep tendon reflexes at the biceps, brachio-radialis and triceps level. This involves tapping of each specified muscle tendon with a neurologic reflex hammer.

b) Fast Urine Pregnancy Test: This is a routine exam performed for women of child bearing age who do not take any birth control prophylaxis.

c) Severity of gleno-humeral subluxation: This is a routine exam performed to assess shoulder subluxation. The space between the glenoid and head of the humerus can be visualized on plain X-rays and measured, in centimeters, to grade severity. This test is done bilaterally.

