q) Non-FES Upper Extremity Exercise: While undergoing the non-FES exercise intervention, the subjects will receive a specific, individualized exercise regimen, consisting of strengthening, stretching, splinting and any other therapeutic interventions that do not use electrical stimulation.. The subjects will remain seated in their primary wheelchair throughout the treatment. The subjects will exercise for 60 minutes/session, three times a week for 4 months.

2. Study duration and number of study visits required of research participants.

The study will last 12 months. The Study Time Line is found in Figure 1, and the Data Collection Schedule in Table 1.

(1) Assessment:

The following post-consent screening will be performed at the Initial visit:

- a. Neurological Exam (about 30 minutes)
- b. Fast Urine Pregnancy Test (about 15 minutes)

The following assessments will be performed at the Initial Visit:

- o. FES Evaluation (about 15 minutes)

The following assessments will be performed at the Initial, 4th month, 9th month, and 12th month Visits:

- c. Severity of gleno-humeral subluxation (about 30 minutes)

The following assessments will be performed at the Initial, 4th month, 5th month, 9th month, and 12th month Visits:

- d. Spasticity measurement (about 15 minutes)
- e. Capabilities of the Upper Extremity test (about 10 minutes)
- f. Jebsen-Taylor Hand Function test (about 15 minutes)
- g. Box and Blocks test (about 15 minutes)
- h. Action Research Arm test (about 20 minutes)
- i. Functional Reach test (about 5 minutes)
- j. Range Of Motion of the upper extremity joints (about 30 minutes)
- k. Numerical Rating Scale (NRS) for pain (about 1 minutes)
- l. Pulmonary Function Test (PFTs) (about 5 minutes)
- m. American Spinal Injury Association (ASIA) exam (about 60 minutes)
- n. Pain and Spasticity Medication inventory (about 10 minutes)

	Initial	4 th Month	5 th Month	9 th Month	12 th Month	Test Evaluator*	Blinded
	5 hours	4 1/2 hours	3 2/3 hours	4 1/4 hours	4 1/4 hours		
Neurological Exam	√					PI, CoI1	No
Fast Urine Pregnancy	√					N1, N2, N3	No
Shoulder X-Ray	√	√		√	√	PI, CoI3	Yes
Modified Ashworth	√	√	√	√	√	PI, CoI1	Yes
CUE	√	√	√	√	√	T1,T6	Yes
JTHF	√	√	√	√	√	T1,T6	Yes
BB	√	√	√	√	√	T1,T6	Yes
ARA	√	√	√	√	√	T1,T6	Yes
FR	√	√	√	√	√	T1,T6	Yes
ROM	√	√	√	√	√	T1,T6	Yes
Pain NRS	√	√	√	√	√	PI, CoI1, SC2	No
PFTs	√	√	√	√	√	N1, N2, N3	No
ASIA	√	√	√	√	√	PI, CoI1	Yes
Meds Inventory	√	√	√	√	√	PI, CoI1, N1, N2, N3, SC2	No
FES Eval	√					T1,T6	No

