* PI: Principal Investigator, CoI1: Co-Investigator 1, CoI3: Co-Investigator 3, T1-7: Therapist 1-7, N1: Nurse 1, N2: Nurse 2, N3: Nurse 3, SC2: Study Coordinator2.

Table 1: Data Collection Schedule

(2) Intervention:

There are a total of 96 visits: 48 FES assisted intervention visits scheduled 1 hour, 3 times a week for 4 months, and 48 non-FES assisted exercise regimen visits scheduled 1 hour, 3 times a week for 4 months.

3. Blinding, including justification for blinding or not blinding the trial, if applicable.

The evaluator will be blinded to group assignment for the following assessment, but we cannot use true blinding due to the intervention's sensory component:

- c. Severity of gleno-humeral subluxation
- d. Spasticity measurement
- e. Capabilities of the Upper Extremity test
- f. Jebsen-Taylor Hand Function test
- g. Box and Blocks test
- h. Action Research Arm test
- i. Functional Reach test
- j. Range Of Motion of the upper extremity joints
- m. American Spinal Injury Association (ASIA) exam

4. Justification of why participants will not receive routine care or will have current therapy stopped.

All subjects will continue to consistently perform their usual (“baseline”) amount of physical activity throughout the study, including performance of lower extremities assisted FES ergometry, home exercise stretching program, cardiovascular conditioning, etc. “Baseline” activity is defined as amount of physical activity performed for at least 1 month prior to enrollment. Routine care will not be interrupted.

5. Justification for inclusion of a placebo or non-treatment group.

Both groups will receive some type of intervention: upper extremity passive ergometry or FES assisted upper extremity ergometry. This way, the effect of FES application will be extracted.

6. Definition of treatment failure or participant removal criteria.

Treatment failure constitutes of:

- Increased pain (more than 3 points increase on the NRS).
- Increased shoulder subluxation (more than 1 cm).
- Decreased range of motion (more than 15 deg).

Subjects will be removed from the study if they:

- Requires significant hospitalization (that would interfere with physiologic processes proposed to be studied through the protocol, i.e. e-stim) – at the discretion of PI.
- Become pregnant.

7. Description of what happens to participants receiving therapy when study ends or if a participant's participation in the study ends prematurely.

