We will be offering FES assisted upper extremity ergometry through our Open Gym program or, if rehabilitative care requires it, though an ongoing, patient tailored program.

b. Devices

1. Name of Test Device:

RT300-SLSA

Manufactured by: Restorative Therapies, Inc
[name]
[name]
[contact]
[contact]

2. Schedule/duration/administration of test device:

The RT300-SLSA Cycle Ergometer is the only device capable of upper extremity cycle ergometry with and without FES, for use in the study.

The device will be used for 1 hour, three times a week, for 4 month,, by both the FES and Control group. For the Treatment group, the device will be programmed to deliver synchronized electrical pulses to the upper extremities. For the Control group, the device will be programmed to drive the cycling of the upper extremities.

Device Risk Assessment: The RT300-SLSA cycle ergometer is a motorized system that allow for purely passive, active, or assisted control over leg or arm cycling. The stimulation system is fully integrated with leg and arm motors (“dynamic motor support”) with unilateral or bilateral stimulation option, allowing for individualized usage for upper and lower extremities. The systems allow for the individual to remain in his/her wheelchair, insuring easy usage across subjects without transfer of the subjects. The speed of cycling can be changed from zero to sixty revolutions per minute (rev/min) and the load (resistance) can be adjusted from zero to 17 Newton-meters (Nm). The system has numerous safety features, such as muscle spasm detection and arm guides, that make it ideal for use in this study. The system have internet connectivity allowing the retrieval of subject settings and the automatic collection of cycling data, ensuring easy use across subjects in this study.

All the ergometers that will be used for this study will be checked and tagged by Johns Hopkins Hospital Clinical Engineering Services (CES). The local IRB of Record does require an approval letter from CES regarding the use of the device in the study. The approval letter is part of the application to the local IRB of Record.

3. FDA Status:

The device is classified as an external functional neuromuscular stimulator (CFR 882.5810). The device is FDA cleared under section 510(k). The device clearance number is K072398.

The device will be used in a research mode that:

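### The protocol gives two different control treatments for the same 48 one-hour visits, and its claim to isolate the effect of FES is supported under only one of them

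*Combined protocol and SAP*

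**What the plan says.** The control treatment is given content in four places.

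- **Exercise.** XI.a.1 (Study design) describes the non-FES period as an individualised regimen of strengthening, stretching and splinting. Item q under XI.a.1(2) repeats this more broadly: "a specific, individualized exercise regimen, consisting of strengthening, stretching, splinting and any other therapeutic interventions that do not use electrical stimulation". It sets the dose: "The subjects will exercise for 60 minutes/session, three times a week for 4 months".
- **Passive cycling.** XI.a.5, the control justification, says: "Both groups will receive some type of intervention: upper extremity passive ergometry or FES assisted upper extremity ergometry". It goes on: "This way, the effect of FES application will be extracted". XI.b.2 has the RT300 used for an hour, three times a week for 4 months, "by both the FES and Control group", and adds: "For the Control group, the device will be programmed to drive the cycling of the upper extremities".

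Elsewhere the control has only a label. The abstract (VI.b), Specific Aim 1 in the Background (VII.a), the Study Design paragraph (VII.b) and the allocation text in XI.a.1(2) call it non-FES exercise. Those four places name ergometry only on the FES side. The visit count in XI.a.2(2) lists "48 non-FES assisted exercise regimen visits scheduled 1 hour, 3 times a week for 4 months". The statistics section (XI.c.1) names one independent variable, FES versus no FES, and says nothing more about the control.

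**The concern.** The comparator determines what staff deliver in the control period and what a difference, or its absence, can mean. Here the procedures section and the device section give different instructions for the same sessions. The only rationale offered for the control belongs to the cycling version.

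If exercise is what is delivered, a positive result could be reported as an effect of electrical stimulation when it reflects arm cycling with motor support compared with other exercise. A null result could be misread in the same way. The analysis could not separate these afterwards, because under that version no condition provides ergometry without FES.

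**Working it through.** **Visit count.** XI.a.2(2) gives 96 intervention visits, 48 in each condition, at three one-hour visits a week for 4 months. Taking 4 months as 16 weeks:

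- 3 × 16 = 48 visits per condition, and 48 + 48 = 96. This reproduces the plan's figures.
- Calendar months would give 3 × (4 × 365.25 / 12 / 7) ≈ 52 visits, so the plan is using 16 weeks.
- Control share: 48 / 96 = 50% of each subject's intervention visits. Because the design is a crossover, this applies to all 24 planned subjects.

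**Can both controls be delivered?**

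- Exercise as in item q: 48 × 1 h = 48 h.
- Cycling as in XI.b.2: 48 × 1 h = 48 h.
- Both in full: 48 + 48 = 96 h, or 6 h a week, against 48 h (3 h a week) scheduled.

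Each description fills the whole control allotment, so they are alternatives.

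**Where each version appears.** Of the places that state content, two give exercise (XI.a.1 and item q) and two give passive cycling (XI.a.5 and XI.b.2). The five label-only places do not define the control. Four of them lean towards exercise by naming ergometry only with FES, but none specifies content.

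**What each version isolates.** FES-period content is from item p.

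| Component | FES period | Control as exercise | Control as passive cycling |
|---|---|---|---|
| Electrical stimulation | Yes | No | No |
| RT300 arm cycling | Yes | Not specified | Yes |
| Motor | Support once muscles fatigue | Not specified | Drives the cycling |
| Strengthening, stretching, splinting | Not specified | Yes | Not specified |
| Session | 1 h, 3 per week, 4 months | Same | Same |

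Against passive cycling, device and schedule are shared, and what differs is stimulation and the work it produces. The second sentence of XI.a.5 follows from that comparison. Against exercise, stimulation, cycling, motor support and exercise content all change together. The label FES versus no FES remains true, but it does not reveal that the rest of the hour differs too.

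**The case against.** The strongest reply is that item q ends with an open clause admitting any other non-electrical therapy, and motor-driven cycling without stimulation literally qualifies. This stands in part: cycling could be one component of the regimen. It does not reconcile the sections, because XI.b.2 gives the device the full hour at every session, leaving no time for the named exercises, and XI.a.5 names ergometry alone.

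A second reply is that XI.a.5 and XI.b.2 are leftovers from another design, since XI.b.2 speaks of treatment and control groups in a crossover. That may be so, but the documents do not say it. If it is so, the protocol's only control justification supports a trial that is not being run.

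Three stronger readings are tempting and unsupported:

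- A reader might infer that most of the protocol adopts the exercise control. Most of those mentions are labels; places that state content split two against two.
- A reader might infer that the stated aims promise an effect of FES alone. None uses that word. The hypothesis in the Background, Hypothesis 1 and the Expected Result all describe FES delivered through ergometry. A comparison of an FES-ergometry programme with individualised exercise is a legitimate trial, and the design statements in VI.b, VII.a and VII.b describe it that way.
- A reader might infer that subjects received mixed controls or that results are biased by some amount. The documents show neither.

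**Conclusion.** The point holds and needs fixing. Four passages of current text define one control period in two ways that cannot both be delivered in full, and the claim to have separated out the FES effect is supported only under passive cycling. The scope is 48 of 96 intervention visits for every subject. That measures reach, and no bias figure is claimed.

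The conclusion does not depend on sample size, power or significance level. It rests on reading the stated hour in item q and in XI.b.2 as the same control session, which the matching frequency and duration support. Figure 1 and the consent form could not be seen, so whether either settles the matter is unknown. The documents also do not show which control has been delivered.

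**What to change.** Name one comparator, identically, in XI.a.1, item q, XI.a.2, XI.a.5 and XI.b.2, and check that the consent form describes the same treatment.

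- **If it is exercise:** delete the reference to passive ergometry and the sentence claiming extraction from XI.a.5, and remove the control-group device text from XI.b.2. Define the factor in XI.c.1, and word the conclusion, as an FES-assisted ergometry programme versus individualised non-FES exercise.
- **If it is passive cycling:** correct XI.a.1 and item q, align the labels in VI.b, VII.a, VII.b, the allocation text and the visit count, and report FES-assisted versus motor-driven passive cycling.

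Rewording the aim and hypothesis is optional.

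The cost is a protocol amendment. Under XVIII.a, a major modification needs the funder's human research protection office to approve it before implementation; any other amendment goes in with the continuing review report. The consent form may need revising. No new subjects or visits are needed, provided a single version has been delivered. If some subjects have already been treated under each version, wording alone will not repair it: record the control each subject actually received and report it. Under the exercise control the price is a narrower conclusion, about a programme and not about stimulation itself.

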XVII. ADVERSE EVENTS.....	28

XVIII. CHANGES TO PROTOCOL	28
a. Protocol Modifications:	28
b. Protocol Deviations:	28
XIX. CONTINUING REVIEW & FINAL REPORT	28
a. Continuing Review Reports:.....	28
c. Final Study Report:.....	29
XX. LITERATURE REVIEW	29
XXI. Appendix: Study Related Documents.....	32
a. Recruitment forms:.....	32
b. Informed Consent forms:.....	32
c. Case Report Forms:	32
d. Serious Adverse Event report forms:.....	32
XXII. Appendix: Medical Device Related Documents.....	33

VI. STUDY INFORMATION**a. Type of Research**

This is Specific Aim 1 of Proposal 08284002 titled "Advanced Restoration Therapies in Spinal Cord Injury".

Specific Aim 1: To determine whether functional electrical stimulation promotes neurological and physical recovery in patients with Spinal Cord Injury.

We will investigate the extent of functional recovery in patients with Spinal Cord Injury (SCI) who receive Functional Electrical Stimulation (FES) in the upper extremities compared with patients who do not receive FES.

b. Abstract

Background: Recent evidence suggests that FES can improve certain functions in the Central Nervous System (CNS) following injury or disease; it can enhance motor recovery, change H reflex and flexor reflex excitability [1-3] and enhance sensory function in chronic SCI [4].

Using FES-based therapies in our clinic, we have seen neurological, physical, and functional improvements. By systematically measuring the impact of FES on functional recovery in individuals with spinal cord related paralysis, we hope to greatly advance our clinical application of FES.

Objective/Hypothesis: To test the hypothesis that patterned neural activity induced by FES enhances recovery of function in the injured spinal cord patients with paralysis.

Study Design SA1: A randomized, controlled, single-blinded, in-subject controlled (A-B type) trial will be performed in patients with SCI receiving an upper extremities non-FES assisted exercise protocol compared with patients receiving upper extremities ergometry in combination with FES. Neurological and functional outcome measures will be obtained at baseline (time 0), after 1st 4 months of intervention (4 months), after 1 month washout (5 months), after 2nd 4 months intervention (9 months), and 3 month after completing the last intervention (12 months).

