make a decision to participate in the study. In addition, the candidate will be allowed to discuss the study's appointment logistics with their own care providers. Any questions the potential subject has about the study will be answered. Once the potential subject agrees to participate, the subject will be enrolled and an initial visit will be set up. The subject consent will be obtained during this initial visit before the post-consent screening is performed.

In the 3 years since opening the International Center for Spinal Cord Injury (ICSCI) in 2005 (05'-08'), we have evaluated and treated over 600 new patients with longstanding SCI (White 63.57%, Black 31.69%, American Indian 0.91%, Hispanic 0.36%, Asian 0.18%, Other 3.28%). Currently we evaluate and treat over 250 new patients annually. Of the new patients with long-standing SCI, 50% are ASIA A and B and of this subgroup, over 10% have a neurological level between C1 and C6. Using projections through 08' and bases of 850 system clients, approximately 85 patients will meet the entry criteria of ASIA A-B, neurological level C1-6 proposed in our study. Furthermore, study entry does not have to be limited to clients already within our ICSCI system. Therefore, based on this availability, we do not anticipate the recruitment of patients to be a substantive barrier to recruitment for this study.

b. Target Population:

We plan to enroll up to 30 subjects with an expected accrued number of subjects of 24 (screening failure of 6). The 24 accrued subjects will be randomized in 2 groups of 12. We are anticipating an attrition rate of 4 subjects maximum.

We plan to enroll both male and female subjects, all ethnic groups.

No specific racial or ethnic groups will be targeted by our recruitment process.

Non-English speaking subjects will not be targeted by our recruitment process.

No vulnerable population is specifically targeted by our recruitment process.

Pregnant women will be excluded from this study.

c. Recruitment Material:

Subject Recruitment Flyer: form given to ICSCI patients that fit the study criteria during a clinic visit, and posted on the ICSCI website (www.spinalcordrecovery.org).

Inclusion/Exclusion Index Card: Laminated index cards with inclusion/exclusion criteria that physician can carry.

Inclusion/Exclusion Wall Listing: Laminated listing with inclusion/exclusion criteria posted in ICSCI clinic rooms that physician can refer to.

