h) Action Research Arm (ARA) test: This is a routine exam performed for people with spinal cord injury. The ARA test observationally assesses upper extremity function (20 items, ordinal scale [57]). Subjects are tested in a seated position, preferably from their wheelchairs, in front of a table. Test items will be laid out on the table and the test conducted per the standardized instructions. The ARA requires subjects to handle objects differing in size, weight and shape.

i) Functional Reach (FR) test: This is a routine exam performed for people with spinal cord injury to evaluate trunk balance. The test is performed by patient reaching forward as far as they can while seated in their wheelchair. The distance traveled by the top of the reference shoulder is measured. 2 practice trials and 1 actual reach test is performed for the purpose of the study.

j) Range Of Motion (ROM) of the upper extremity joints: This is a routine exam performed for people with spinal cord injury. The Range Of Motion of the shoulder, elbow, wrist, and metacarpal-phalangeal joints will be measured via goniometry. Subjects are tested in a seated position, preferably in their wheelchairs. The desired joint is isolated and moved through the maximum available range of motion. Once the end range is reached, joint excursion is measured with a goniometer.

k) Numerical Rating Scale (NRS) for pain: This is a routine exam performed for people with spinal cord injury. Subjects report how much pain they are having by choosing a number from 0 (no pain) to 10 (the worst pain imaginable) (ordinal scale, [48]).

l) Pulmonary Function Test (PFTs): This is a routine exam performed for people with spinal cord injury. Three respiratory functions will be measured. Vital Capacity (VC) is the maximal amount of air that can be exhaled after a maximal inhalation. Negative Inspiratory Force (NIF) is the ability to take a deep breath in and to generate a cough strong enough to clear secretions. Peak Cough Flow (PCF) measures the expiratory muscle force and the ability to cough.

m) American Spinal Injury Association (ASIA) exam: This is a routine exam performed for people with spinal cord injury. The ASIA exam assesses motor function at 10 key muscles in the body and light touch and pinprick sensation at 28 key points on each side of the body. It is also used to classify injury level and severity (ordinal scale, [49]).

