n) Pain and Spasticity Medication inventory: This is a routine exam performed for people with spinal cord injury. Pain and antispasticity medications dose will recorded.

o) FES Evaluation: This is a routine exam performed for people with spinal cord injury prior to receiving FES. Therapist 1 or 6 will test the different muscles that are targeted for this study to achieve the best motor response to FES, and maintain subject comfort. Depending on the neurological level of the subject, the muscles are: supraspinatus; infraspinatus; teres major and minor; anterior, middle, or posterior deltoid; biceps; and triceps.

(2) Intervention:

The subjects will be randomly assigned, in a one-to-one ratio, either to group 1, which will first engage in the FES assisted ergometry followed by the non-FES assisted exercise, or to group 2, which will first engage in the non-FES assisted exercise followed by the FES assisted ergometry.

p) FES Upper Extremity Cycle Ergometry: While undergoing the FES assisted ergometry intervention, the subjects will use an RT300-SLSA upper extremity ergometer configured with FES. Electrode placement will be individually optimized to produce smooth cycling, as measured by crank symmetry, average stimulation level, expended energy per hour, and muscle stiffness. Parameters of stimulation current will also be individually optimized to achieve the best motor response (frequency of 10 to 100 Hz, pulse duration of 50 to 500 μ s, and amplitude of 10 to 140 mA). Silver mesh self-adhesive surface electrodes will be used to conduct the stimulation. They will activate some combination of the following muscles, depending on the neurological level at which they are applied: supraspinatus; infraspinatus; teres major and minor; anterior, middle, or

posterior deltoid; biceps; and triceps. Target cycling speed will be 20 rpm, with a resistance of 0.965Nm. The subjects will warm up between 2 and 10 minutes depending on muscle stiffness or spasms, actively cycle with FES for 1 hour, and cool down of 2 minutes. The ergometer software will be set to provide motor support once muscle fatigue has been reached so the subjects can continue. The subjects will remain seated in their primary wheelchair throughout the treatment. The subjects will cycle for 60 minutes/session, three times a week for 4 months.

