- 1] allows the stimulation of our proposed list of upper extremity muscles (supraspinatus; infraspinatus; teres major and minor; anterior, middle, or posterior deltoid; biceps; and triceps), which is more than the standard set of muscles (bilateral biceps, triceps and supraspinatus).
- 2] allows to change the timing of the stimulation (On/Off) to produce a smooth cycling motion.

4. FDA approved use description:

The device FDA indication for use are:

1. Relaxation of muscle spasms
2. Prevention or retardation of disuse atrophy
3. Increasing local blood circulation
4. Maintaining or increasing range of motion

5. IDE Info:

Not applicable

c. Study Statistics

1. Primary outcome variable.

Independent Variables

FES or no FES

Dependent Variables: to be measured at 0, 4, 5, 9 and 12months

Severity of gleno-humeral subluxation, measured by X-ray (not measured at 5 months).

Spasticity of the pectoralis, biceps, triceps, and long finger flexor muscles, measured with the Modified Ashworth.

Functional movement of the shoulder, measured with the Capabilities of the Upper Extremity (CUE) test.

Hand function, measured with the Jebsen-Taylor Hand Function (JTHF) and Box and Blocks (BB) tests.

Upper limb function measured with the Action Research Arm test (ARA) test.

Range Of Motion of the upper extremity joints (of the shoulder, elbow, wrist, and fingers/thumbs), measured with goniometry.

Pain, measured with the Numerical Rating Scale (NRS).

Neurological function, measured with the American Spinal Injury Association (ASIA) exam.

2. Secondary outcome variables.

Not applicable

3. Statistical plan including sample size justification and interim data analysis.

Data Analysis: Data will be collected in accordance with each instrument's standardized instructions, with the evaluator being blinded to group assignment. To obtain consistency and facilitate interpretation of the data, we will use means and standard deviations (SDs) to describe normally as well as non-normally distributed variables. Appropriate post-hoc statistical analysis will be used to compare between group means and repeated measures. Baseline tests of homogeneity will be used *a priori*. If statistically significant differences are found after the subjects are randomized to the two groups, they will be corrected in the post-hoc analysis. Results will be considered significant at $P<0.05$.

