Accurate and complete study records will be maintained and made available to representatives of the U.S. Army Medical Research and Materiel Command. These representatives are authorized to review research records as part of their responsibility to protect human research volunteers. Research records will be stored in a confidential manner so as to protect the confidentiality of subject information.

XIII. RISK AND INJURY

a. Risks, Risk Management:

All assessments and intervention sessions will be supervised by the Principal Investigator.

For all the study procedures, the risks and risk management are defined in the sections below.

1. Assessment Risks:

a) Neurological Exam: During testing, the subject might experience pain induced by hitting/tapping of the arm, but usually, the sensation experienced is a quick, non-painful touching sensation. To minimize the risk, one of the study team member trained in the procedure will perform the test.

b) Fast Urine Pregnancy Test: There is the possibility of psychological stress occurring if testing shows that the subject may be pregnant. To minimize the risk in the event that pregnancy test results are positive, the result will be disclosed to the subject. If the subject is uncomfortable with this arrangement, his/her consent to participate in this study is not recommended.

c) Severity of gleno-humeral subluxation: The subjects receive ionizing radiation due to the diagnostic bilateral shoulder X-ray procedures they receive at the Initial, 4th Month, 9th Month, and 12th Month visit. The Total Effective Dose from the procedures is 0.4 rem. This is more than the 0.3 rem that the average person in the United States gets each year from natural sources like the sun, outer space, air, food and soil. It is less than the 5 rems of radiation that is allowed each year for people who are exposed to radiation in their jobs. To minimize the risk, pregnant women are excluded from the study.

d) Spasticity Measurement: There is a risk of eliciting spasms during the test. Subjects will feel a quick pull of the muscle, which might be painful at times. To minimize the risk, one of the study team member trained in the procedure will perform the test.

e) Capabilities of the Upper Extremity (CUE) test: There are no known risks associated with this test.

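### The only pain criterion for treatment failure and early stopping cannot be met from an NRS reference score of 7 or higher: a narrow safety gap, cheap to close

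*Combined protocol and SAP*

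**What the plan says.** Pain is rated on the NRS. Section XI.a.1, item k, defines the scale: "Subjects report how much pain they are having by choosing a number from 0 (no pain) to 10 (the worst pain imaginable". The schedule in XI.a.2 and Table 1 places it ("Numerical Rating Scale (NRS) for pain (about 1 minutes") at months 0, 4, 5, 9 and 12, and Table 1 marks the assessment as not blinded. Section XI.c.1 lists it among the primary dependent variables: "Pain, measured with the Numerical Rating Scale (NRS".

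The treatment-failure definition in XI.a.6 and the early stopping rules in XI.c.4 carry the same single pain item: "Increased pain (more than 3 points increase on the NRS". The other items in the two sections concern shoulder subluxation, range of motion, hospitalization, pregnancy and failure to follow directions. Neither section has an absolute pain level, a relative change or a clause for intolerable pain.

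Neither section names the visit from which the increase is counted. The abstract (VI.b) does call time 0 the baseline: "Neurological and functional outcome measures will be obtained at baseline (time 0". Section VIII sets no upper limit on pain at entry. Its only pain-related item, VIII.a(i), asks that pain and antispasticity medication doses be held stable.

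**The concern.** An absolute rise on a bounded scale is limited by the room left above the starting score. A subject who moves from 0 to 4 meets the criterion. A subject who moves from 7 to the top of the scale does not. The explicit numeric trigger therefore stops working where pain is already worst.

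What is at stake is safety monitoring. Section XIII.a.2 names pain at the stimulation site as a risk of FES, and each subject is scheduled for 96 one-hour sessions. For a subject with a high reference score, the written rule never signals that pain has worsened and never classes that subject as a pain failure.

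**Working it through.** **Inputs.** Scale 0 to 10 (XI.a.1, item k). Criterion: rise strictly greater than 3 (XI.a.6 and XI.c.4). Planned subjects: 24 (IX.b). The plan gives a threshold but no derived figure to reproduce.

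**Reachability.** Largest rise = 10 − reference. The criterion can be met only if 10 − reference > 3, that is, if the reference is below 7.

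| Reference | Largest rise | More than 3 possible? |
|---|---|---|
| 0 to 5 | 10 to 5 | yes |
| 6 | 4 | yes |
| 7 | 3 | no |
| 8 | 2 | no |
| 9 | 1 | no |
| 10 | 0 | no |

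Half-point scores give the same cutoff of 7.0. The result is stated by reference score, so it holds whichever visit supplies the reference. A rule of 3 points or more would make 7 reachable but not 8 to 10.

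**Possible worsening steps on whole-number scores.** From 0 to 6 there are 10+9+8+7+6+5+4 = 49, of which 7+6+5+4+3+2+1 = 28 meet the rule. From 7 to 10 there are 3+2+1+0 = 6, of which none does. The 21 misses from 0 to 6 reflect the chosen threshold; the 6 from 7 to 10 reflect the ceiling. These are counts of scale values, not of subjects.

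**Subjects affected.** The documents give no pain distribution, so the share p with a reference of 7 or higher is an assumption. Expected number = 24 × p. Upper bound on scheduled comparisons under the fix (months 4, 5, 9 and 12) = 4 × 24 × p.

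| Assumed p | Expected subjects | Scheduled comparisons, at most |
|---|---|---|
| 0% | 0 | 0 |
| 2% | 0.5 | 1.9 |
| 5% | 1.2 | 4.8 |
| 10% | 2.4 | 9.6 |
| 20% | 4.8 | 19.2 |
| 30% | 7.2 | 28.8 |

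**Choice of reference.** Take scores of 0, 3, 3 and 6 at months 0, 4, 5 and 9. Counted from month 0, the month 9 rise is 6 − 0 = 6, which meets the rule. If the reference were reset at month 5, the rises would be 3 − 0 = 3 in the first period and 6 − 3 = 3 in the second, and the rule would never be met. With the lower of the month 0 and month 5 scores (0), the rise is again 6 and the rule is met.

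**The case against.** The strongest reply accepts the arithmetic and disputes the consequence. No affected subject is shown to exist. Pain is looked at on a fixed schedule: the NRS is taken at all five visits, with a medication inventory alongside ("Pain and antispasticity medications dose will recorded"). Section XIII.a states: "All assessments and intervention sessions will be supervised by the Principal Investigator". Stimulation is limited to what the subject tolerates, whatever the NRS score. A subject whose pain forces a dose increase departs from VIII.a(i), and the inventory would show it. Subjects may withdraw at any time, routine care continues, and the medical monitor reviews serious adverse events and unanticipated problems.

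Most of this stands, and it rules out a stronger reading. A reader might infer that subjects with severe pain are unprotected; the documents do not support that. What remains is that none of these safeguards is a pain criterion for failure or stopping. The tolerance limit acts within an FES session and does not cover the non-FES period. Stimulation-site pain is already a listed risk, so worsening that is not serious may fall outside what the monitor must review.

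A reader might also infer that the gap distorts the efficacy results. It does not, on the plan as written: treatment failure is not a dependent variable in XI.c.1 and is not used in XI.c.3, where the variable analysed is the NRS itself.

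Finally, the NRS case report form and the consent form are listed in the appendix, but their content is not available here. Either may contain instructions for handling pain.

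**Conclusion.** The point holds as a narrow safety gap. That the criterion is unreachable from 7, 8, 9 and 10 is exact: it needs only the 0 to 10 range and the strict inequality. That such subjects can enter follows from the absence of a pain limit in section VIII.

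The practical size is not established. The number affected may be zero, and every share above is an assumption. No count of sessions saved or harms avoided can be claimed, because XI.c.4 does not say when the rule is to be applied. With no role for treatment failure in the analysis and partial safeguards in place, this is a cheap improvement of minor severity. Confidence is high in the arithmetic and low in any estimate of impact.

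**What to change.** In both XI.a.6 and XI.c.4:

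- Keep the more-than-3-point rule unchanged. Do not reset its reference at month 5, which would lose accumulated worsening, as the example above shows. If a reference is named, use the lower of the month 0 score and the score at the start of the current period.
- Add that, for a reference of 7 to 10, documented investigator review with discretion to stop is required on any NRS increase at a scheduled assessment or, at 10, on reported worsening or a need for more pain medication. Make no stop automatic: the NRS is unblinded and is a primary dependent variable, so a one-point change should not by itself remove a subject.

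The cost is a sentence or two in each section. NRS and medication dose are already collected at every visit. Each affected subject has at most four scheduled comparisons with the reference (months 4, 5, 9 and 12); reports of worsening from a subject at 10 could add reviews between visits. Months 9 and 12 fall after study treatment has ended, so a scheduled review can alter treatment only at months 4 and 5.

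The downside is some extra reviews and possibly an occasional discretionary stop on an unblinded outcome, each 1/24 = 4.2% of the sample. The plan states: "We are anticipating an attrition rate of 4 subjects maximum". Extra stops alone would reach that figure only if 4/24 = 16.7% of subjects both had a reference of 7 or higher and were stopped on review.
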